### **Retrospective:**

- The control group for this study will be obtained from a retrospective chart review of electronic health records of patients with incomplete cleft lip who underwent surgery without any presurgical interventions. These records will be obtained from the Texas Cleft-Craniofacial Team. Only records of infants with non-syndromic unilateral incomplete cleft lip will be qualified for this study. To eliminate variability, only patients treated by one pediatric plastic surgeon ([name]) will be included. All patients with complete cleft lip, or diagnosed with a syndrome, or had any surgeries not provided by the same plastic surgeon (prior to the initial cheiloplasty) will be excluded. Any records with incomplete data or necessary photographs will also be excluded.

IRB NUMBER: HSC-DB-20-0311

- Necessary photographs are to include those taken at the initial visit soon after birth and those at the visit immediately prior to lip surgery. Photographs need to include those taken in the standard anterior-posterior view, profile view, and worms-eye view.
- Linear measurements will be obtained with a ruler and registered in millimeters. A goniometer will be used to measure angles.

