## **Outcome Measures (Endpoints) and Time Points**

### **Primary Outcome Measures:**

- Soft tissue changes as indicated by columellar angle measured from extraoral clinical photographs
  - Time points: initial time of examination with study team, time of surgery
  - Soft tissue changes as indicated by nostril width measured from extraoral clinical photographs
    - Time points: initial time of examination with study team, time of surgery
    - Soft tissue changes as indicated by nostril height measured from extraoral clinical photographs
      - Time points: initial time of examination with study team, time of surgery
      - Soft tissue changes as indicated by width of the cleft lip measured from extraoral clinical photographs
        - Time points: initial time of examination with study team, time of surgery

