**Retrospective:**

- The Texas Cleft-Craniofacial Team photo database will be queried for patients with incomplete unilateral cleft lip who have undergone cleft lip repair from 2015-2020.
  - Inclusion criteria
    - Unilateral cleft lip with or without cleft palate
    - Patients of a single surgeon ([name])
    - Patients with complete photographs: □ After birth, first visit

IRB NUMBER: HSC-DB-20-0311

- At cleft lip repair (3-4 months)
- Post-operative cleft repair (about 1 year of age)
  - Exclusion criteria
    - Bilateral cleft lip or complete unilateral cleft lip
    - Patients operated on by other primary surgeons
- Patients with incomplete photo records will be evaluated to determine if the patient should be excluded

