**Study Procedures**

**Retrospective:**

- Electronic health records of infants with unilateral incomplete cleft lip and/or palate who underwent or is undergoing surgery within the University of Texas Health Science Center will be reviewed. Patients whose clefts are associated with a syndrome will be excluded along with those that have had any other presurgical interventions. Qualifying participants must have had surgical repair after January 2015 or will have surgery before January 2021. Charts with incomplete patient data, inaccessible contact of caregiver, inadequate records or both pre- and post-op photographs in the necessary angles will be excluded.

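### Control records are screened for photographs as whole records, under conflicting rules, so controls usable for some primary endpoints can be lost or kept at discretion

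*Combined protocol and SAP*

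**What the plan says.** The rules for photographs of control infants stand in three places.

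- **Study Design, Retrospective:** "Any records with incomplete data or necessary photographs will also be excluded". On timing: "Necessary photographs are to include those taken at the initial visit soon after birth and those at the visit immediately prior to lip surgery". On views: "Photographs need to include those taken in the standard anterior-posterior view, profile view, and worms-eye view". Three views at two visits make six images, and the unit excluded is the record.
- **Study Population, Retrospective:** "Patients with incomplete photo records will be evaluated to determine if the patient should be excluded". No criteria for that evaluation are given. The same list asks for a third, post-operative set: "Post-operative cleft repair (about 1 year of age".
- **Study Procedures, Retrospective:** charts with incomplete data are excluded, as are those with "inadequate records or both pre- and post-op photographs in the necessary angles will be excluded". The photograph clause is garbled as worded, but the exclusion again acts on the chart.

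Under Primary Outcome Measures there are four separate endpoints: columellar angle, nostril width, nostril height and cleft lip width. Each is taken at the initial examination and at surgery. Two of them read "Soft tissue changes as indicated by columellar angle measured from extraoral clinical photographs" and "Soft tissue changes as indicated by width of the cleft lip measured from extraoral clinical photographs". The source is extraoral photographs throughout, and no section names the view from which any endpoint is read. Nor does any section provide for an analysis in which a control counts for some endpoints but not others.

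**The concern.** The exclusion rule is written for the record, while the outcomes are four separate measurements. Nostril width and cleft lip width are side-to-side distances, which a profile image cannot show. A control with readable frontal or worms-eye images at both visits but no profile image has what those two endpoints need. Under the Study Design rule that infant is nevertheless dropped from all four. Under the Study Population rule the infant may be kept or dropped, and nothing says on what grounds.

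This matters because the two arms are not exposed to the rule equally. The study itself photographs treated infants in all three views, whereas control images come from an archive. The filter therefore works mainly on one arm of a non-randomised comparison. The treated arm is capped at 10, so the control arm is the place where precision can still be gained. A criterion unrelated to the endpoint adds avoidable selection on archive completeness, and an unstated criterion adds selection that nobody can later describe.

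**Working it through.** **Step 1: is there a figure in the plan to reproduce?** No. The Statistics section gives 10 prospective infants, justified as a pilot and by feasibility. The documents do not state the number of controls, the number of eligible charts or the share of missing images. What follows is a range under stated assumptions.

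**Step 2: the rules side by side.**

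| Section (Retrospective part) | Unit | Action on an incomplete photo set |
|---|---|---|
| Study Design | record | excluded |
| Study Population | patient | evaluated, no criteria |
| Study Procedures | chart | excluded for incomplete data or inadequate records; photo clause unclear |

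The rules conflict, and none works by endpoint.

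**Step 3: inputs.** From the documents: 3 views × 2 visits = 6 images, and 10 treated infants. Assumed: 30 eligible charts; each image present independently with probability p = 0.95, 0.90 or 0.80; equal SD in the two groups.

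**Step 4: share of controls retained.** With k images required, the share is p^k. The six-image rule has k = 6, an endpoint read from one view has k = 2, and an endpoint needing two views has k = 4.

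| p | k = 6 | k = 4 | k = 2 |
|---|---|---|---|
| 0.95 | 0.735 | 0.815 | 0.902 |
| 0.90 | 0.531 | 0.656 | 0.810 |
| 0.80 | 0.262 | 0.410 | 0.640 |

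**Step 5: expected controls, n = 30 × p^k.**

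| p | k = 6 | k = 4 | k = 2 |
|---|---|---|---|
| 0.95 | 22.1 | 24.4 | 27.1 |
| 0.90 | 15.9 | 19.7 | 24.3 |
| 0.80 | 7.9 | 12.3 | 19.2 |

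**Step 6: half-width of the 95% interval for the group difference, in SD units.** The formula is t(0.975; n + 8) × √(1/10 + 1/n). For p = 0.90 and k = 6 this is 2.064 × √(0.1 + 1/15.94) = 2.064 × 0.4034 = 0.833. For k = 2 it is 2.036 × √(0.1 + 1/24.3) = 2.036 × 0.3757 = 0.765. The reduction is 1 − 0.765/0.833, or about 8%.

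| p | k = 6 | k = 4 (reduction) | k = 2 (reduction) |
|---|---|---|---|
| 0.95 | 0.779 | 0.764 (1.8%) | 0.751 (3.5%) |
| 0.90 | 0.833 | 0.796 (4.4%) | 0.765 (8.1%) |
| 0.80 | 1.011 | 0.888 (12.2%) | 0.800 (20.9%) |

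**Step 7: the lower bound.** If photographs go missing only as whole visits, a control lacking one view lacks all three at that visit. The three-view requirement then removes nobody whom a one-view requirement would keep, and the gain is zero. Partial clustering lies between zero and the table.

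**Step 8: a second illustration.** With 40 charts, p = 0.90 and a true difference of 1.0 SD, expected controls are 21 under the six-image rule, 26 for a two-view endpoint and 32 for a one-view endpoint. Exact two-sided t-test power at 0.05 is 0.71, 0.74 and 0.77.

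**The case against.** Four objections carry weight.

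- **The drop is not automatic.** A reader of Study Design alone might infer that every control with a missing view is certainly lost. The documents do not support that, because Study Population allows such a patient to be kept. This objection stands. What it leaves is a conflict between a fixed rule and a discretionary rule without criteria.
- **No endpoint is mapped to a view.** A reader might infer that no primary endpoint needs all three views. That is firm only for the two widths, and only as regards the profile view. For columellar angle and nostril height the documents settle nothing. Study Procedures also allows for calculated ratios, which could draw on more than one image. This stands, and the missing mapping is part of the defect.
- **The loss may be small or nil.** It depends on independence and on an assumed pool. The 21% figure needs one image in five to be missing singly, and the 10 treated infants limit precision in every scenario. This stands, and no large loss can be claimed.
- **One consistent control set, held to the same views as the treated infants, is defensible.** Study Population says the criteria are deliberately strict so as to reduce variability. Inclusion by endpoint would let the control set differ between endpoints, and it would still select on having images at both visits. This is fair, but reporting the complete-record analysis as a sensitivity check keeps what that approach offers.

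**Conclusion.** The concern holds in a limited form. The control-record rules contradict one another and act on the whole record or patient. If the fixed rule is followed, controls usable for nostril width and cleft lip width can be discarded for want of a profile image or an unrelated chart item. If the case-by-case rule is followed, retention is discretionary. Either way the selection bears mainly on the archival arm. Its direction is unknown: that infants with full archives differ in severity or follow-up is possible, but the documents do not show it.

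The cost in precision runs from nil (whole visits missing) to about 4%, 8% or 21% of interval width for a one-view endpoint, when 5%, 10% or 20% of images are missing independently. For a two-view endpoint the figures are about 2%, 4% and 12%. These rest on the assumed 30 charts and on independence. The change is worth making mainly because it replaces conflicting rules with one objective rule at very little cost.

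**What to change.** 1. Reconcile the Retrospective parts of Study Design, Study Population and Study Procedures into a single rule. All three need editing, because chart-level exclusion would otherwise survive in Study Procedures.
2. Assign the view or views for each primary endpoint before any image is read and without knowledge of outcome.
3. Include a control in an endpoint's analysis whenever readable images in the assigned view or views exist at both presurgical visits. Do not require views or chart items that the endpoint does not use. The post-operative set falls in this class for the primary endpoints, none of which has a post-operative time point.
4. Report the number of controls for each endpoint, and the exclusions with reasons.
5. Give the analysis restricted to complete records as a sensitivity check.

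The cost is protocol wording and some additional archived images to measure. The drawback is that the number of controls may differ between endpoints, so each comparison must carry its own count.

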## **Study Design**

Newborns with incomplete cleft lip and parents that consent to presurgical intervention of DynaCleft® + Nasal Elevator system will be compared to a retrospective group of infants born with incomplete cleft lip treated by the UTHealth Texas Cleft-Craniofacial Team that have received surgical intervention and have existing presurgical photographs available for examination. The primary outcome will be to compare craniofacial soft tissue changes measured from extraoral clinical photographs obtained at the initial examination to the ones obtained prior to surgery. The child's guardian who completed the DynaCleft® therapy will also be asked to complete an infant quality of life assessment survey.

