**Prospective:**

- The study population for the prospective aspect will include recruited newborns with untreated unilateral incomplete cleft lip. Patients whose clefts are associated with a syndrome will be excluded. DynaCleft® + Nasal Elevator therapy will be discussed with parent(s) as a presurgical orthopedic option while awaiting primary cleft lip surgical repair that typically occurs between the ages of 3 to 6 months. Informed consent for participation in the study must be obtained from the patients' parents.
- Study duration will be up to three months of presurgical intervention (similar to the existing nasoalveolar molding NAM appliance protocols).
- Patients will be recruited by the Texas Cleft-Craniofacial team. ○ Infants that match the inclusion criteria will be invited to participate in this study.
- Photographs are to be taken at initial visit prior to presurgical intervention and later at completion of the DynaCleft® therapy immediately prior to lip surgery. Angles to be pictured are to include the standard anterior-posterior, profile, and worms-eye view.
- Linear measurements will be obtained with a ruler and registered in millimeters. A goniometer will be used to measure angles.
- The parents of infants enrolled in the DynaCleft® study will be asked to complete an Infant and New Parent Quality of Life survey at the initial and final visits. Components from this survey were adopted from the Infant and Toddler Quality of Life Questionnaire and the CDC Breastfeeding and Infant Practices Questionnaire (see attachments).

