**Prospective:**

- One evaluator will obtain all photographs to be evaluated in this study, examine Electronic Health Records, and collect necessary data and measurements onto a password protected Microsoft Excel Spreadsheet. Measurements to be recorded may include columellar angles, nostril width, nostril height, width of the lip cleft, etc. While most of the information can be gathered directly from the photographs, some factors may require calculations such as soft tissue ratios if need be. The primary investigator will be blinded to whether or not subject has participated in the DynaCleft® study. Data are to be measured twice and results compared to account for accuracy. Participants are identified on the spreadsheet solely by an assigned code. Factors to be recorded will also include general biographical and physical information (age, gender, weight, etc.), duration of treatment and compliance of caregivers.
- Interaction with

IRB NUMBER: HSC-DB-20-0311

participants in the DynaCleft® study will involve one monthly visit up until date of surgery, usually between 3 to 6 months of age. Each appointment is estimated to be

an hour long to allow for assessment of the orthopedic, recording of information, and addressment of any concerns. The initial and last visits may require more time due to obtainment of necessary photographs. Participants will be required to receive DynaCleft® treatment for at least 2 months before lip surgery to qualify. Additionally, parents of infants with incomplete unilateral cleft lip that choose not to use the DynaCleft® + Nasal Elevator system but are willing to complete the infant quality of life assessment at time of surgery will be allowed to complete the survey. All images obtained in this study will be stored in a password protected and encrypted computer. Prospective patient images will be stored in the Electronic Health Record. Images will be de-identified.

- Parents will be asked to complete the Infant and New Parent Quality of Life questionnaire at both the initial visit and date of surgery.

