### **Statistics**

- Each individual patient will be monitored for changes during either participation in the experimental group or control group. A paired Student's t-test will be used to compare changes within the individual patient.
- Comparisons between the experimental and control group will be made with an appropriate statistical test depending on the distribution of data points (parametric or non-parametric).
- Up to 20 patients will be approached for recruitment for the prospective portion of this study. After the 10th patient is enrolled in the study, no other patients will be approached.
- We plan to enroll 10 subjects. This sample size collection was determined as an appropriate amount for a pilot study to test the effectiveness of this treatment. Similar studies using DynaCleft® have utilized similar sample sizes. Additionally, this number was based on the number of potential patients we can enroll within a twelve-month period.
- P-values less than 0.05 will be considered significant.

IRB NUMBER: HSC-DB-20-0311

- Termination of the pilot trial will occur after the 10th patient completes treatment.

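### Three of the four primary endpoints are ruler readings in mm from photographs, with no scale or calibration required; in unscaled images a magnification difference would count as soft-tissue change

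*Combined protocol and SAP*

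**What the plan says.** Primary Outcome Measures lists one angle (columellar) and three lengths (nostril width, nostril height, cleft lip width), all taken from photographs at the initial examination and at surgery. For example: "Soft tissue changes as indicated by nostril width measured from extraoral clinical photographs".

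The Retrospective and Prospective parts of Study Design give the same rule for lengths: "Linear measurements will be obtained with a ruler and registered in millimeters". Control infants are those who "have existing presurgical photographs available for examination"; treated infants get new photographs.

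What is standardised is the time points and the views. For new images: "Angles to be pictured are to include the standard anterior-posterior, profile, and worms-eye view". The retrospective part names the same three views. Neither part mentions a scale in the frame, camera distance, calibration or correction for magnification.

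Three statements in Study Procedures (Prospective) bear on the point:
- "One evaluator will obtain all photographs to be evaluated in this study"
- "some factors may require calculations such as soft tissue ratios if need be"
- "Data are to be measured twice and results compared to account for accuracy"

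Statistics plans a paired t-test of change within each patient and a between-group test chosen by the distribution of the data, with significance at p below 0.05.

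**The concern.** A ruler laid on a photograph measures the image, not the face. The reading is in true millimetres only if the scale of that image is known. If it is not, the recorded change mixes tissue change with any difference in magnification between the two photographs.

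The stated safeguards do not reach this error. Both readings of one photograph share its magnification, so they can agree closely and both be wrong. Blinding deals with reader bias, not image scale. A single photographer does not fix magnification, and for archived images, obtaining them can only mean retrieving them.

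The effect depends on the pattern of the magnification differences:
- Random differences add noise to the change scores and cost precision.
- A systematic shift between visits biases the within-patient paired test, even when both groups share it.
- A shift that differs between groups also biases the between-group comparison.

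The columellar angle is not affected by uniform magnification.

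**Working it through.** **Inputs from the documents.** Three of four primary endpoints are lengths; 10 treated infants; significance level 0.05 (taken as two-sided). The plan gives no length, SD, expected difference, scale error or number of controls, so it has no figure to reproduce.

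**Assumed inputs.** Length W = 10 mm; SD of true change SD0 = 1 or 2 mm; between-group difference 1.5 mm; 20 controls; scale error e = 5% or 10% per photograph.

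**1. Random scale error, between-group test.** Independent errors at the two visits add variance 2(We)² to the change score:

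total SD = √(SD0² + 2(We)²)

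For SD0 = 1 and e = 5%: √(1 + 2 × 0.5²) = 1.22 mm. For e = 10%: √(1 + 2 × 1²) = 1.73 mm. For SD0 = 2 the totals are 2.12 and 2.45 mm. Power of the two-sample t-test (noncentral t, 10 against 20):

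| SD0 | no scale error | e = 5% | e = 10% |
|---|---|---|---|
| 1 mm | 96% | 86% | 58% |
| 2 mm | 46% | 42% | 33% |

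The loss depends on length. With SD0 = 1 mm, power at 5% / 10% error is 94% / 86% for a 5 mm length and 73% / 36% for a 15 mm length. In simulations with no true difference, the false-positive rate under random error stayed at 4.6% to 5.4%.

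**2. Systematic shift between visits, paired test.** The false change is W × shift: 10 × 5% = 0.5 mm, or 10 × 10% = 1.0 mm. With no true change and n = 10, the noncentrality is (false change / SD) × √10. For 0.5 mm and SD 1 mm this is 1.58.

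| SD of change | 5% shift | 10% shift |
|---|---|---|
| 1 mm | rejects 29% | rejects 80% |
| 2 mm | rejects 11% | rejects 29% |

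The nominal rate is 5%. A shift common to both groups roughly cancels in the between-group test. A shift in one group only adds the same 0.5 or 1.0 mm to the group difference.

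**3. Does a ratio help?** Uniform magnification cancels within one image: (10 × 1.1)/(8 × 1.1) = 1.25 = 10/8. But the denominator brings its own reading error and its own change over time. Simulated power (20,000 trials per setting, SD0 = 1 mm, difference 1.5 mm, 20 controls, 5% scale error, reading SD 0.5 mm, mean of two readings):

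| Length / denominator | SD of denominator change | uncalibrated mm | ratio |
|---|---|---|---|
| 10 mm / 10 mm | 0 | 82% | 87% |
| 10 mm / 10 mm | 1 mm | 82% | 67% |
| 10 mm / 25 mm | 1 mm | 82% | 88% |

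With these inputs the ratio gains with a long or stable denominator and loses with one that is short and changing.

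**The case against.** The strongest reply is that the harm is hypothetical. The rule about a ruler is compatible with a ruler in the frame, and the documents never say that images are unscaled. That stands. A reader might infer that the three endpoints are invalid or that the results will be biased; the documents support neither. They show only that following the plan does not guarantee a known scale.

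Second, every figure above rests on assumed inputs, and the loss runs from slight (46% to 42%) to large (96% to 58%). That also stands: the figures show what could happen and do not estimate what will.

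Third, this is a pilot: "This sample size collection was determined as an appropriate amount for a pilot study to test the effectiveness of this treatment". No power is stated, so none is breached. But that sentence also says that effectiveness is to be tested, and a p-value threshold is set, so the measurement still has to mean what it says.

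Fourth, ratios are already allowed. They are, but no ratio, denominator or trigger is defined, so the choice between mm and ratio could be made after results are seen.

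Two further inferences go too far. One is that bias needs a shift that differs between groups; the planned paired test does not need that. The other is that nothing can be done once photographs are taken. Absolute mm cannot be recovered from an unscaled image, but a ratio within the image can still be computed.

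**Conclusion.** The concern holds as a gap in the measurement plan. Three of four primary endpoints are in mm from photographs, with no required scale and no fixed rule for ratios. If images are unscaled, random magnification differences cost precision. A systematic shift between visits distorts the paired test even when both groups share it, and a shift that differs by group distorts the group comparison. Whether any of this occurs depends on the images, which the documents do not describe. The size rests wholly on the assumed lengths, SDs, scale errors and number of controls. This is an inexpensive improvement that should be made before measurement starts. It does not show that the trial is invalid.

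**What to change.** 1. **Study Design, Prospective:** require a scale in the plane of the measured feature in every new study photograph.
2. **Study Design, Retrospective:** before any measurement, check whether the archived control images carry a usable scale at both visits.
3. **If every image in both groups can be calibrated:** convert each to true mm and keep mm as primary. State that calibrated mm still includes growth between visits.
4. **Otherwise:** replace the optional wording on ratios in Study Procedures with one rule for both groups, fixed before measurement, and align Primary Outcome Measures with it. Use cleft-side to non-cleft-side ratios for nostril width and height. Divide cleft lip width by one named, long facial distance visible in the same view at both visits. Use the mean of the two planned readings. Report mm only for scaled images, as supportive.
5. Keep the columellar angle in degrees.

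**Cost.** A scale in each new photograph, one archive check and some wording; under step 4, an extra reading for each denominator. Ratios describe relative rather than absolute size and can lose power with a short or changing denominator, so calibrated mm comes first where possible. A scale visible only in new images could also reveal the group. Cropping it protects the blinding only if an existing team member other than the measuring evaluator prepares the coded images. If that cannot be arranged, state it as a limitation.
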